10.42 Expedited Reporting Requirements for IND/IDE Agents

10.421 Expedited Reporting Requirements for Adverse Events that Occur on Studies under an IND/IDE within 30 Days of the Last Administration of the Investigational Agent/Intervention¹

FDA REPORTING REQUIREMENTS FOR SERIOUS ADVERSE EVENTS (21 CFR Part 312)				
NOTE: Investigators MUST immediately report to the sponsor ANY Serious Adverse Events, whether or not they are considered related to the investigational agent(s)/intervention (21 CFR 312.64) An adverse event is considered serious if it results in ANY of the following outcomes:				

 1) Death 2) A life-threatening adverse event 3) An adverse event that results in inpatient hospitalization or prolongation of existing hospitalization for ≥ 24 hours 4) A persistent or significant incapacity or substantial disruption of the ability to conduct normal life functions 5) A congenital anomaly/birth defect. 6) Important Medical Events (IME) that may not result in death, be life threatening, or require hospitalization may be considered serious when, based upon medical judgment, they may jeopardize the patient or subject and may require medical or surgical intervention to prevent one of the outcomes listed in this definition. (FDA, 21 CFR 312.32; ICH E2A and ICH E6). 				
ALL SERIOUS adverse events that meet the above criteria MUST be immediately reported within the timeframes detailed in the table below.				
Hospitalization	Grade 1 Timeframes	Grade 2 Timeframes	Grade 3 Timeframes	Grade 4 & 5 Timeframes
Resulting in Hospitalization ≥ 24 hrs	7 Calendar Days			24-Hour 3 Calendar Days
Not resulting in Hospitalization ≥ 24 hrs	Not required		7 Calendar Days	
NOTE: Protocol specific exceptions to expedited reporting of serious adverse events are found in section 10.41 of the protocol.				
Expedited AE reporting timelines are defined as:				

 ○ “24-Hour; 3 Calendar Days” - The AE must initially be reported within 24 hours of learning of the AE, followed by a complete expedited report within 3 calendar days of the initial 24-hour report. ○ “7 Calendar Days” - A complete expedited report on the AE must be submitted within 7 calendar days of learning of the AE. 				
¹ Serious adverse events that occur more than 30 days after the last administration of investigational agent/intervention and have an attribution of possible, probable, or definite require reporting as follows:				

Expedited 24-hour notification followed by complete report within 3 calendar days for:

- All Grade 4, and Grade 5 AEs

Expedited 7 calendar day reports for:

- Grade 2 adverse events resulting in hospitalization or prolongation of hospitalization
- Grade 3 adverse events

10.43 Additional instructions:Special reporting requirements for Millennium

AEs may be spontaneously reported by the patient and/or in response to an open question from study personnel or revealed by observation, physical examination, or other diagnostic procedures. Any clinically relevant deterioration in laboratory assessments or other clinical finding is considered an AE. When possible, signs and symptoms indicating a common underlying pathology should be noted as one comprehensive event. For serious AEs, the investigator must determine both the intensity of the event and the relationship of the event to study drug administration.

AEs which are serious must be reported to Millennium Pharmacovigilance (or designee) from the first dose of study drug through 30 days after administration of the last dose of ixazomib. Any SAE that occurs at any time after completion of ixazomib treatment or after the designated follow-up period that the sponsor-investigator and/or sub-investigator considers to be related to any study drug must be reported to Millennium Pharmacovigilance (or designee). In addition, new primary malignancies that occur during the follow-up periods must be reported, regardless of causality to study regimen, for a minimum of three years after the last dose of the investigational product, starting from the first dose of study drug. All new cases of primary malignancy must be reported to Millennium Pharmacovigilance (or designee).

Planned hospital admissions or surgical procedures for an illness or disease that existed before the patient was enrolled in the trial are not to be considered AEs unless the condition deteriorated in an unexpected manner during the trial (e.g., surgery was performed earlier or later than planned). All SAEs should be monitored until they are resolved or are clearly determined to be due to a patient's stable or chronic condition or intercurrent illness(es).

Since this is an investigator-initiated study, the principal investigator, [name], also referred to as the sponsor-investigator, is responsible for reporting serious adverse events (SAEs) to any regulatory agency and to the sponsor- investigator's EC or IRB.

Regardless of expectedness or causality, all SAEs (including serious pretreatment events) must also be reported in English to Millennium Pharmacovigilance (or designee):

Fatal and Life Threatening SAEs within 24 hours of the sponsor-investigator's observation or awareness of the event

All other serious (non-fatal/non-life-threatening) events within 4 calendar days of the sponsor-investigator's observation or awareness of the event

See below for contact information for the reporting of SAEs to Millennium Pharmacovigilance.

The sponsor-investigator must fax or email the SAE Form per the timelines above. A sample of an SAE Form will be provided.

The SAE report must include at minimum:

- **Event term(s)**
- **Serious criteria**
- **Intensity of the event(s):** Sponsor-investigator's or sub-investigator's determination. Intensity for each SAE, including any lab abnormalities, will be determined by using the NCI CTCAE version specified in the protocol, as a guideline, whenever possible. The criteria are available online at [REDACTED]
- **Causality of the event(s):** Sponsor-investigator's or sub-investigator's determination of the relationship of the event(s) to study drug administration.

Follow-up information on the SAE may be requested by Millennium.

Intensity for each SAE, including any lab abnormalities, will be determined by using the NCI CTCAE version used at your institution, as a guideline, whenever possible. The criteria are available online a [REDACTED]

In the event that this is a multisite study, the sponsor-investigator is responsible to ensure that the SAE reports are sent to Millennium Pharmacovigilance (or designee) from all sites participating in the study. Sub-investigators must report all SAEs to the sponsor-investigator so that the sponsor-investigator can meet his/her foregoing reporting obligations to the required regulatory agencies and to Millennium Pharmacovigilance, unless otherwise agreed between the sponsor-investigator and sub-investigator(s).

Relationship to all study drugs for each SAE will be determined by the investigator or sub-investigator by responding yes or no to the question: Is there a reasonable possibility that the AE is associated with the study drug(s)?

Sponsor-investigator must also provide Millennium Pharmacovigilance with a copy of all communications with applicable regulatory authorities related to the study product(s), as soon as possible but no later than 4 calendar days of such communication.

SAE and Pregnancy Reporting Contact Information

Fax Number: [REDACTED]

Suggested Reporting Form:

- SAE Report Form (provided by Millennium)
- US FDA MedWatch 3500A: [REDACTED]
- Any other form deemed appropriate by the sponsor-investigator

Product Complaints

A product complaint is a verbal, written, or electronic expression that implies dissatisfaction regarding the identity, strength, purity, quality, or stability of a drug product. Individuals who identify a potential product complaint situation should immediately contact Medical Information and report the event. Whenever possible, the associated product should be maintained in accordance with the label instructions pending further guidance from a Millennium Quality representative.

For Product Complaints

- Phone: [name] ([name])

- E-mail: [contact]
- [contact]
- Hours: Mon-Fri, 8 a.m. – 6 p.m. ET

Product complaints in and of themselves are not AEs. If a product complaint results in an SAE, an SAE form should be completed and sent to Millennium Pharmacovigilance

Special reporting requirements for Celgene

Celgene Drug Safety Contact Information:

Celgene Corporation
Global Drug Safety and Risk Management

Investigator Reporting Responsibilities

The conduct of the study will comply with all FDA safety reporting requirements.

IND Annual Reports

If the FDA has granted an IND number, it is a requirement of 21 CFR 312.33, that an annual report is provided to the FDA within 60-days of the IND anniversary date. 21 CFR 312.33 provides the data elements that are to be submitted in the report. The Annual Report should be filed in the study's Regulatory Binder, and a copy provided to Celgene Corporation as a supporter of this study as follows.

Celgene Corporation
Attn: Medical Operations

All adverse experience reports must include the patient number, age, sex, weight, severity of reaction (e.g. mild, moderate, severe), relationship to drug (e.g. probably related, unknown relationship, definitely not related), date and time of administration of test medications and all concomitant medications, and medical treatment provided. The investigator is responsible for evaluating all adverse events to determine whether criteria for "serious" and as defined above are present. The investigator is responsible for reporting adverse events to Celgene as described below.

Expedited reporting by investigator to Celgene

Serious adverse events (SAE) are defined above. The investigator must inform Celgene in writing using a Celgene SAE form or MEDWATCH 3500A form of any SAE within 24 hours of being aware of the event. The written report must be completed and supplied to Celgene by facsimile within 24 hours/1 business day. The initial report must be as complete as possible, including an assessment of the causal relationship between the event and the investigational product(s), if available. Information not available at the time of the initial report (e.g., an end date for the adverse event or laboratory values received after the report) must be documented on a follow-up report. A final report to document

resolution of the SAE is required. The Celgene tracking number (PO-MM-PI-002443) and the institutional protocol number should be included on SAE reports (or on the fax cover letter) sent to Celgene. A copy of the fax transmission confirmation of the SAE report to Celgene should be attached to the SAE and retained with the patient records.

10.5 Other Required Reporting

10.51 Procedures for Reporting Drug Exposure During Pregnancy and Birth Events

If a woman becomes pregnant or suspects that she is pregnant while participating in this study, she must inform the investigator immediately and permanently discontinue study drug. The sponsor-investigator must fax a completed Pregnancy Form to the Millennium Department of Pharmacovigilance or designee (see Section 10.43). The pregnancy must be followed for the final pregnancy outcome.

If a female partner of a male patient becomes pregnant during the male patient's participation in this study, the sponsor-investigator must also immediately fax a completed Pregnancy Form to the Millennium Department of Pharmacovigilance or designee (see Section 10.43). Every effort should be made to follow the pregnancy for the final pregnancy outcome.

Suggested Pregnancy Reporting Form:

- Pregnancy Report Form

Use form available from the CTEP protocol development page:

[Redacted]

Mayo Clinic Cancer Center (MCCC) Institutions: Provide copies, along with the UPIRTSO cover sheet, by fax [Redacted] to the MCCC Regulatory Affairs Unit (RAU) Risk Information Specialist who will determine and complete IRB reporting. The RAU will submit to the MCCC SAE Coordinator and the MCCC IND Coordinator to determine if FDA submission is needed.

Millennium Pharmacovigilance Fax Number: [Redacted]

10.6 Required routine reporting

Adverse events to be graded at each evaluation and pretreatment symptoms/conditions to be evaluated at baseline per the CTCAE v4.0 grading unless otherwise stated in the table below:

SYSTEM ORGAN CLASS	Adverse event/Symptoms	Baseline	Each evaluation
Investigations	Creatinine increased	X	X
	Neutrophil count decreased	X	X
	Platelet count decreased	X	X
General disorders and administration site conditions	Fatigue	X	X
Gastrointestinal Disorders	Nausea	X	X
	Vomiting	X	X
	# of Stools	X	
	Diarrhea		X
	Constipation		X
Infections and infestations	Sepsis	X	X
Blood and lymphatic system disorders	Febrile neutropenia	X	X
Skin and subcutaneous tissue disorders	Rash, maculopapular	X	X
Nervous system disorders	Peripheral sensory neuropathy	X	X
	Peripheral motor neuropathy	X	X

10.62 Submit via appropriate MCCC Case Report Forms (i.e., paper or electronic, as applicable) the following AEs experienced by a patient and not specified in Section 10.5:

10.621 Grade 2 AEs deemed *possibly, probably, or definitely* related to the study treatment or procedure.

10.622 Grade 3 and 4 AEs regardless of attribution to the study treatment or procedure.

10.623 Grade 5 AEs (Deaths)

- Any death within 30 days of the patient's last study treatment or procedure regardless of attribution to the study treatment or procedure.
- Any death more than 30 days after the patient's last study treatment or procedure that is felt to be at least possibly treatment related must also be submitted as a Grade 5 AE, with a CTCAE type and attribution assigned.

10.63 Refer to the instructions in the Forms Packet (or electronic data entry screens, as applicable) regarding the submission of late occurring AEs following completion of the Active Monitoring Phase (i.e., compliance with Test Schedule in Section 4.0).

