6.8 Baseline symptoms

All required baseline symptoms (see Section 10.62) must be documented and graded.

6.9 Study drug is available on site.

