8.11 Instruction for initiation of a new cycle of therapy

A new cycle of treatment may begin on the scheduled Day 1 of a new cycle if:

- The ANC is $\geq 1000/\mu\text{L}$
- The platelet count is $\geq 50,000/\mu\text{L}$
- Any other non-hematologic treatment -related adverse event that may have occurred has resolved to \leq Grade 1 or baseline severity.

If these conditions are not met on Day 1 of a new cycle, the subject will be evaluated weekly and a new cycle of therapy will be held until the toxicity has resolved as described above.

If any drug dosing was halted during the previous cycle and was restarted with a one-level dose reduction without requiring an interruption for the remainder of the cycle, then that reduced dose level will be initiated on Day 1 of the new cycle.

If any drug dosing was omitted for the remainder of the previous cycle or if the new cycle is held due to known hematologic toxicity newly encountered on the scheduled Day 1, then the new cycle will be started with a one-level dose reduction. If a new cycle of therapy cannot be restarted within 4 weeks of the scheduled Day 1 due to non-resolution of drug related toxicities, the patient will be removed from protocol therapy and will go to event monitoring.

→ → Use the NCI Common Terminology Criteria for Adverse Events (CTCAE) version 4.0* unless otherwise specified ← ←

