16.32 Secondary Outcome Analyses

- 16.321 Type of response will be differentiated as biochemical vs. extramedullary disease, as defined in Section 11.6. Biochemical response will be defined as a response by serum M-protein, urine M-protein, or serum FLC assay parameters. For biochemical response, the response rate will be estimated by the number of responders divided by the number of evaluable patients who have measurable disease by serum M-protein, urine M-protein, or serum FLC assay at baseline. Extramedullary response will be defined as a response by extramedullary plasmacytoma or plasma cell count parameters. For extramedullary response, the response rate will be estimated by the number of responders divided by the number of evaluable patients. Exact binomial confidence intervals will be calculated.
- 16.322 Progression-free survival is defined as the time from registration to the earliest date of documentation of disease progression or death due to any cause. The distribution of progression-free survival will be estimated using the method of Kaplan-Meier.
- 16.323 Adverse Events: All eligible patients that have initiated treatment will be considered evaluable for assessing adverse event rate(s). The maximum grade for each type of adverse event will be recorded for each patient, and frequency tables will be reviewed to determine patterns. Additionally, the relationship of the adverse event(s) to the study treatment will be taken into consideration.

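### Constipation is graded at every on-treatment evaluation but has no required baseline grade, so persisting pre-existing constipation cannot be separated by grade in the toxicity table

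*Combined protocol and SAP*

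**What the plan says.** Section 10.6 sets out routine adverse event collection: "Adverse events to be graded at each evaluation and pretreatment symptoms/conditions to be evaluated at baseline per the CTCAE v4.0 grading". Read to its end, the sentence allows exceptions: "pretreatment symptoms/conditions to be evaluated at baseline per the CTCAE v4.0 grading unless otherwise stated in the table below". The table lists 13 graded events and one count, the number of stools. Eleven of the graded events are marked both at baseline and at each evaluation. Diarrhea and constipation are marked at each evaluation only, and the stool count at baseline only.

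Section 6.8 adds: "All required baseline symptoms (see Section 10.62) must be documented and graded". It covers required symptoms only, and baseline constipation is not marked as required.

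Two later sections use this information:

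- Section 16.323 (adverse event analysis): "The maximum grade for each type of adverse event will be recorded for each patient, and frequency tables will be reviewed to determine patterns". The next sentence says that "the relationship of the adverse event(s) to the study treatment will be taken into consideration". Treatment-emergence is not defined, and no comparison with baseline is specified.
- Section 8.11 (start of a new cycle): "Any other non-hematologic treatment -related adverse event that may have occurred has resolved to" Grade 1 or less "or baseline severity".

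Section 15.17 lists constipation as very common (10% or more) with ixazomib, and Section 15.27 does the same for pomalidomide.

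**The concern.** Goal 2.21 is to determine the toxicities associated with the regimen. In a single-arm trial each patient's own pre-treatment state is the only internal comparator. For eleven of the solicited events that comparator is collected as a grade. For diarrhea there is at least a stool count with an evident link to it. Constipation has neither.

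Because constipation is solicited at every evaluation, its lower grades enter the data. Under Section 10.62, by contrast, an unlisted event is submitted only from related Grade 2 upward. A patient who had mild constipation before the first dose and still has it in Cycle 1 therefore appears in the 16.323 frequency table exactly as a patient with new constipation does. At stake is the interpretability of one reported rate, for a symptom expected with two of the three study drugs, together with the recorded basis for one branch of the new-cycle rule.

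**Working it through.** The documents state no figure for this point, so there is none to reproduce. The check is a reading of the sections side by side, followed by an illustration of size.

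**Reading the table.** Of the 13 graded events, 11 have both marks, which leaves 13 − 11 = 2. These are diarrhea, with the stool count as apparent partner, and constipation, with no evident partner. The documents do not say that the stool count serves diarrhea alone, but in either case it is a count and not a CTCAE grade.

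**Looking for the grade elsewhere.** The Section 4.0 test schedule has a complete medical history within 30 days before registration, and adverse event monitoring and a physical exam within 14 days. None of these entries names constipation or requires a grade for it. Section 6.8 does not add one.

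**Where the missing grade matters in 8.11.** The rule covers treatment-related non-hematologic events and is already met at Grade 1 or less. The baseline branch is needed only when related constipation is still at Grade 2 or higher on the scheduled Day 1. In that case no required recorded grade exists to compare with.

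**Illustration of size.** Inputs:

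- e, the on-drug rate: 57/173 = 32.9%, the 33% shown in Table 1-3 for oral ixazomib combinations. The single-agent figure in Table 1-2 is 46/201 = 23%.
- b, the share with constipation before treatment: not in the documents. Assumed 10% to 20%, independent of e, and assumed to persist to at least one evaluation.
- n: 27 evaluable patients, or 30 in total, at full accrual (Section 16.22). The 16.323 denominator is eligible patients who started treatment, so at full accrual it should lie in about this range.

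Recorded rate = 1 − (1 − e)(1 − b). Net excess over e = b(1 − e), with 1 − e = 0.671.

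- b = 0: recorded 32.9% (8.9 of 27); no excess.
- b = 10%: recorded 39.7%; excess 27 × 0.10 × 0.671 = 1.8, or 30 × 0.10 × 0.671 = 2.0 patients.
- b = 20%: recorded 46.4%; excess 27 × 0.20 × 0.671 = 3.6, or 30 × 0.20 × 0.671 = 4.0 patients.

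The gross number with constipation before treatment would be 30 × 0.10 = 3 to 30 × 0.20 = 6. About a third of them would have had an on-drug event anyway at the 33% rate, so the net figure is the relevant one.

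**The case against.** Four objections have force.

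- **The table is an express exception.** The opening sentence of 10.6 yields to its table. A reader might infer that 10.6 contradicts itself; it does not. This is a gap in what is collected.
- **Other information exists.** A reader might infer that nothing is ascertained before drug starts, or that pre-existing cases can never be separated. The documents do not support that. History, physical exam and adverse event monitoring come before registration, a stool count is taken at baseline, and 16.323 considers attribution, using the five categories of Section 10.3. What remains is that attribution is a judgement. For a symptom expected with two study drugs, a baseline grade is the most direct evidence for that judgement.
- **8.11 still works.** A reader might infer that its baseline-severity test cannot be applied to constipation. That goes too far. The rule does not refer to 10.6, it covers many events absent from that table, and an investigator can draw on the history. The gap is only that no required grade stands behind this branch for related constipation of Grade 2 or higher.
- **16.323 adjusts no event for baseline.** Pre-existing fatigue or neuropathy enters the same table unadjusted, so a baseline mark alone would not change the constipation row. This is right, and it is why the fix has two parts. For the eleven events with both marks the comparison could still be made from collected data; for constipation it could not.

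**Conclusion.** The point holds as a minor gap in data collection and reporting. Constipation is the only solicited event in 10.6 with neither a required baseline grade nor an evident baseline partner. Because 16.323 reports maximum grade without reference to baseline, persisting pre-existing cases are mixed into its rate.

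The size is about 2 to 4 patients out of 27 to 30. That rests on an assumed pre-treatment prevalence of 10-20%, on independence from the 33% on-drug rate, on persistence of the symptom into treatment, and on a rate taken from other ixazomib combinations. If patients with prior constipation are also more likely to develop it on drug, the overlap is larger and the excess smaller.

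A reader might infer an effect on the trial's decisions. There is none to speak of. The response endpoint, its 0.10 significance level and its 0.90 power do not use these data. The early safety rule in 16.4 and the stopping rule in 16.52 count only related non-hematologic events, at Grade 3 or higher and Grade 4 or higher respectively.

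**What to change.** Make two changes together:

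1. In the Section 10.6 table, add a Baseline mark for constipation, so that a CTCAE grade is recorded before treatment.
2. In Section 16.323, report solicited events both as maximum grade and as worsening from baseline grade, alongside attribution. Diarrhea would use the baseline stool count as its reference.

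For patients already treated, state in the report that no baseline constipation grade was required, so that the worsening column is read accordingly. While Section 10.6 is open, correct the cross-reference in Section 6.8: it points to 10.62, but the baseline column is in the 10.6 table.

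The cost is one extra field on the baseline form and one extra column in the adverse event table. No treatment rule, sample size or decision rule changes.
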